6.1 General visit setting

Briefly, five visit points are scheduled for this study. Visit 1 will be the screening visit. Visit 2 will be performed on the day of Gn initiation. Visit 3 will be carried out on the day of ET. Visit 4 will be carried out two weeks after ET to confirm biochemical pregnancy. Visit 5 will be carried out five weeks after ET to confirm clinical pregnancy. Follow-up after delivery will be conducted through web or telephone contact to ascertain the live birth outcomes of participants (**Figure 1**).

[figure not shown]

Figure 1. Study flowchart. Gn, gonadotropin; hCG, human chorionic gonadotropin; ZYP, Zishen Yutai Pill.

6.2 Screening visit

If the patient express interest toward the clinical trial, a screening visit will be performed. Patients will be informed about the study thoroughly. During the screening visit, the following procedures will be completed.

- (1) Going through all the inclusion and exclusion criteria. Obtaining the signed informed consent form.
- (2) Collecting baseline information, including age, medical record number, and birth date.
- (3) Reviewing the medical history, including infertility history, childbearing history, gynecological surgery history, disease history and menstrual information.
- (4) Carrying out a physical examination and gynecologic examination.
- (5) Measuring the baseline sex hormones, including E₂, FSH, LH, prolactin (PRL), and testosterone (T).
- (6) Reviewing the previous ET/FET cycle record.
- (7) Dispensing information.

6.3 Gn initiation visit

During the Gn initiation visit, the following procedures will be completed.

- (1) Adverse events and treatment (if necessary).
- (2) Medication on Gn initiation, including type, name, initiation dose.
- (3) Serum hormone levels, including E₂, FSH, LH, and P₄.
- (4) Dispensing and return information.

6.4 ET visit

During the ET visit, the following procedures will be completed.

- (1) Adverse events and treatment (if necessary).
- (2) Summary of COH including type, name and total amount.
- (3) B-mode ultrasound and basal serum hormonal level.

- (4) Information about semen collection, embryo development, embryo transfer information.
- (5) Information about the medicines used in luteal phase support, including name, dose, duration, and total amount.
- (6) Dispensing and return information.

6.5 Biochemical pregnancy test visit

At 14 days after transplantation, a biochemical pregnancy test will be performed.

- (1) Adverse events and treatment (if necessary).
- (2) Serum level of β -HCG pregnancy test (β -HCG >50 IU/L is defined as biochemical pregnancy).
- (3) Drug dispensing and return information will be recorded.

6.6 Clinical pregnancy test visit

If the pregnancy test is positive, transvaginal ultrasonography will be performed 3 weeks later to confirm clinical pregnancy.

- (1) Adverse events and treatment (if necessary).
- (2) Clinical pregnancy will be confirmed using B-mode ultrasound. Clinical pregnancy is defined as the presence of intrauterine gestation sac with fetal motion under transvaginal ultrasonography.
- (3) Drug return information will be recorded.
- (4) If a clinical pregnancy is confirmed, contact information and intention of delivery hospital will be checked.

6.7 Delivery visit

When the participant is preparing to deliver, the investigator will collect the delivery information and infant information according to the form designed for this visit. The delivery information mainly includes the delivery mode and pregnancy complications. The neonate information mainly includes gender, birth weight and length, birth

defects, admission to newborn intense care unit within 1 month and stillbirth.

7. Physical examination

A physical examination will be conducted on all participants by the corresponding investigator. The parameters include height, weight and they will be recorded to the nearest 0.1 cm, 0.1 kg. Height and weight will be measured without shoes, and patients will be dressed in light clothing.

8. Transvaginal ultrasound scan

An ultrasound scan with a transvaginal probe will be carried out. Uterine dimension, endometrial thickness and type, bilateral ovarian dimension, and follicle number will be measured through the ultrasound scan. The uterine size will be determined at the widest diameter. The investigator will determine endometrial types. Endometrial thickness is the largest anterior-posterior measurement of the endometrium in the sagittal plane. Ovarian dimension is measured by analysis of the largest plane of the ovary in two dimensions. In addition, antral follicle count (AFC) will be recorded.

9. Laboratory tests

Hormone and pregnancy tests will be performed at the local laboratories. In addition, blood work will be performed on screening visit, Gn initiation visit, hCG trigger day, and 2 weeks after ET. The blood sample (5 ml) will be collected with an anticoagulant tube and stored at -80°C for further analysis.

10. Outcome measures

The live birth rate is the primary outcome. The secondary outcomes will include counts and rates of oocytes/embryos (oocytes retrieved, 2 pro-nuclei zygotes, cleavage zygotes, available embryos, high-quality embryos), pregnancy outcomes (rates of biochemical pregnancy, implantation, clinical pregnancy and miscarriage),

incidences of maternal, fetal and neonatal complications, neonate information (newborn birthweight and length, congenital malformation) (14).

Live birth is defined as delivery of any viable infants after 28 weeks of gestation.

The number of oocytes retrieved will be defined as the total number of oocytes retrieved through ultrasound-guided transvaginal aspiration. The rate of oocytes retrieved will be defined as the number of retrieved oocytes divided by the number of follicles with a diameter ≥ 10 mm on the HCG injection day. Matured oocytes will be defined as those with pronuclei or polar bodies observed on Day 1 after oocyte retrieval in IVF patients, or as the number of MII oocytes on the day of oocyte retrieval in ICSI patients. Cleavage oocytes will be defined as the number of fertilized oocytes that undergo cleavage on Day 2 after oocyte retrieval. The rate of cleavage will be defined as the number of cleaved embryos divided by the number of fertilized oocytes (2PN + 1PN + multiple PN). Available embryos will be defined as the sum of the number of embryos transferred and the number of embryos frozen. The rate of available embryos will be defined as the number of available embryos divided by the number of cleaved oocytes. High-quality embryo will be defined according to the day of embryo transfer, following the Istanbul consensus and Gardner criteria, Day 2: 4 cells, cell fragments $<10\%$ and no multi-nucleus; Day 3: 8 cells, cell fragments $<10\%$, no multi-nucleus; Day 5: stage 4 blastocyst, grade A inner cell mass, grade A trophectoderm (12,13). The rate of high-quality embryos will be defined as the number of high-quality embryos divided by the number of available embryos.

Biochemical pregnancy will be defined as positive when β -HCG >50 IU/L. Implantation rate will be defined as the number of gestational sacs per the number of embryos transferred. Clinical pregnancy will be defined as the presence of intrauterine gestation sac with fetal motion under transvaginal ultrasonography. Miscarriage rate will be calculated among patients with biochemical pregnancies and patients with clinical pregnancies.

Incidence of maternal, fetal and neonatal adverse events were assessed, including moderate or severe OHSS, gestational diabetes mellitus (GDM), gestational

hypertension, postpartum hemorrhage, preterm delivery, congenital anomalies, puerperal infection, stillbirth, neonatal jaundice, neonatal infection, neonatal death, ectopic pregnancy, and low birth weight infant. The definitions of these safety indexes were shown in **Table 6**.

Table 6. Definitions of safety outcomes

Safety outcome	Definitions
Ovarian hyperstimulation syndrome (OHSS)	OHSS is defined according to the Golan criteria. Mild OHSS is diagnosed by the presence of abdominal distension and discomfort with or without nausea, vomiting, and/or diarrhea. Moderate OHSS is diagnosed when ultrasonographic ascites were present in addition to the above features. Severe OHSS is diagnosed when there is clinical evidence of ascites and/or hydrothorax or breathing difficulties with or without hemoconcentration, coagulation abnormalities, and diminished renal function.
Pregnancy loss	Pregnancy loss is defined as pregnancies that eventuate in spontaneous abortion or therapeutic abortion that occurred throughout pregnancy.
Gestational diabetes mellitus	GDM is defined as carbohydrate intolerance of variable severity with onset or first recognition during pregnancy as determined from the diagnosis in the obstetrical medical record.
Gestational hypertension	Gestational hypertension is defined as blood pressure $\geq 140/90$ mmHg with negative proteinuria, which appeared during pregnancy and returned to normal 12 weeks after delivery. It may have upper abdominal discomfort or thrombocytopenia.
Postpartum hemorrhage	Postpartum hemorrhage is defined as the loss of 500 ml of blood or more after completion of the third stage of labor.
Preterm delivery	Delivery of a fetus at less than 37 and more than 28 weeks gestational age.
Congenital anomalies	Congenital anomalies are defined as structural or functional anomalies that occur during intrauterine life, including minor and major anomalies.
Puerperal infection	Any bacterial infection of the genital tract after delivery and during puerperium.

Stillbirth	The absence of signs of life at or after birth.
Neonatal jaundice	Neonatal jaundice is yellowing of the skin and other tissues of a newborn infant.
Neonatal infection	Neonatal infection is defined as a variety of infections in neonates caused by bacteria, fungi, viruses, etc., as determined from the diagnosis in the neonatal medical record.
Neonatal death	The death of a live-born neonate within 28 days after delivery.
Low birth weight infant	Neonatal birth weight \leq 2500 g.
Ectopic pregnancy	Ectopic pregnancy is one in which the blastocyst implants at any site other than the endometrial lining of the uterus cavity.

11. Timeline and recruitment plan

The planned duration of recruitment will be 24 months with 12 centers. The enrollment target of our clinical trials is 1466 randomized participants. The number of participants taken in each center will be allocated according to the actual situation. The treatment period may need about 3 months and another 9 months to trace the pregnancy outcome. In short, a total of 36 months will be required to complete this trial, from initial recruitment to pregnancy outcome period.

12. Statistical analysis plan

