1.6 Publication committee

Members of the publication committee include [name], [name].

2. Background

The deferment of childbirth has emerged as a significant concern in recent years. Over the past forty years, the prevalence of primiparity at age of 35 years or older increased by 9 times (1). Advanced maternal age (AMA), defined as pregnancy at 35 years or older, is commonly linked with reduced fecundity (2,3). AMA patients are more inclined to the use of assisted reproductive technology (ART), including in vitro fertilization (IVF) and intracytoplasmic sperm injection (ICSI) (4). Nonetheless, their pregnancy outcomes are typically less favorable compared to their younger counterparts, as aging adversely affects both oocyte quality and ovarian reserve (5).

Traditional Chinese Medicine (TCM) has been employed for over two millennia in the treatment of a myriad of conditions, including infertility (6). A representative formula for the treatment of infertility is the Zishen Yutai Pill (ZYP). ZYP is a patent Chinese medicine invented by [name] (7). Since its market debut in 1983, ZYP was renowned for its therapeutic effects on threatened miscarriage and recurrent miscarriage. ZYP is consisted of fifteen Chinese medicine, including Cuscutae Semen, Ginseng Radix et Rhizoma, Dipsaci Radix, Taxilli Herba, Eucommiae Cortex, Morindae Officinalis Radix, Cervi Cornu Degelatinatum, Codonopsis Radix, Atractylodis Macrocephalae Rhizoma, Asini Corii Colla, Lycii Fructus, Rehmanniae Radix Praeparata, Polygoni Multiflori Radix Praeparata, Artemisiae Argyi Folium, and Amomi Fructus (8).

In previous clinical practice, the administration of ZYP was observed to enhance the ovulation and pregnancy rate, while decrease the miscarriage rate among patients with polycystic ovary syndrome (PCOS) (9). Another clinical report had suggested that oral intake of ZYP around the luteal phase could significantly increase the embryo implantation rate (10). Our previous multicenter, placebo-controlled, randomized clinical trial had suggested that the intervention of ZYP among advanced maternal aged women could significantly increase the clinical pregnancy rate during ART.

However, this analysis constituted a post hoc subgroup analysis, lacking the statistical power to detect the between-group difference. Therefore, the design of the current

study aims to provide data regarding the efficacy and safety of ZYP in IVF/ICSI for the AMA patients.

3. Objectives

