The present study aims to investigate the efficacy and safety of ZYP on live birth rates among AMA infertile women during IVF/ICSI-ET. The primary objective is to determine the difference of live birth rate between the ZYP and placebo group. The secondary outcomes will include counts and rates of oocytes/embryos (oocytes retrieved, 2 pro-nuclei zygotes, cleavage zygotes, available embryos, high-quality embryos), pregnancy outcomes (rates of biochemical pregnancy, implantation, clinical pregnancy and miscarriage), incidences of maternal, fetal and neonatal complications, and neonate information (newborn birthweight and length, congenital malformation).

4. Participants

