5.2 Randomization and blinding

The participants will be randomized 1:1 to receive double-blind single-dummy monotherapy with placebo or ZYP using the permuted block randomization method. The randomization will be stratified by the age (35-37, 38-39 and 40-42) by following the Human Fertilisation and Embryology Authority (11). The web-based Interactive Response Technology system is managed by independent statisticians, guiding drug dispensing.

Patients, investigators and clinical staff performing this trial will be blinded to treatment allocation. The package, appearance and odor are the same in the placebo and ZYP. The allocation and detailed information of randomization will be kept by the independent statisticians managing the Interactive Response Technology system. Blinding will be maintained until the completion of the analysis. Unblinding will be allowed in case of a medical emergency. The cause and time of unblinding will be recorded in detail and signed by the treating physicians.

When all live birth information is retrieved, the computer system will disclose the allocation.

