5.3.3 Oocyte retrieval and embryo transfer

When the diameter and counts of follicles meet the criteria (two leading follicles \geq 18 mm; or \geq 3 follicles \geq 17 mm; or \geq 4 follicles \geq 16 mm), ovulation will be triggered by injecting human chorionic gonadotropin (HCG). Testing of serum FSH, LH, E₂ and P₄ levels will be conducted on HCG injection day. Oocyte collection will be performed 36 hours later. Luteal support will be started on oocyte retrieval day. Fertilization will be achieved by conventional IVF or ICSI with the husband's semen. On day 3 to day 5 after oocyte retrieval, one to three embryos will be transferred.

High-quality embryos is defined according to Istanbul consensus and Gardner criteria (12, 13).

Day 2	4 cells, cell fragments <10%, no multi-nucleus
Day 3	8 cells, cell fragments <10%, no multi-nucleus
Day 5	stage 4 blastocyst, grade A inner cell mass, trophectoderm at grade A

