12.2 Sample size estimation

In our previous clinical research, the live birth rate was 0.42 per embryo transfer in ZYP treated group and 0.33 per embryo transfer in placebo control group among AMA women. By assuming the same live birth rates, a sample size of 454 women in each group can provide a power of 80% at a significance level of 0.05. According to previous study, the dropout rate before ET was 15% and the cycle cancellation rate was 23% in AMA women. For this trial, a total rate of 38% (dropout and cancellation) is considered in the sample size calculation. Therefore, a total of 1466 participants

will be recruited in this study, 733 participants in each group.

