12.3 Type of analysis

We will utilize an intent-to-treat approach to examine differences in the live birth rates for the first embryo transfer cycle in the two treatment arms in the primary analysis by the Pearson χ^2 test. Safety parameters and secondary efficacy parameters, such as pregnancy rate, miscarriage rate and other rates, will be analyzed using the Pearson χ^2 test or Fisher exact test as appropriate. Secondary efficacy parameters, including the counts and rates of oocytes/embryos, will be analyzed using the Mann-Whitney U test.

For the primary and secondary outcomes, we will also perform analysis in the per-protocol set (PPS), excluding those who have major protocol deviation(s), cancel cycle or do not complete the pre-set minimum exposure dosage of the assigned study drug (at least 80% compliance), from the ITT population. Subgroup analysis will be conducted as stratified by age (35-37, 38-39, 40-42).

Prior to unblinding, missing value in the primary outcome (live birth) and secondary outcomes (biochemical pregnancy, clinical pregnancy) in the ITT analysis will be imputed as not having an event.

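### Section 12.3 gives no test or unit of analysis for implantation; its likeliest reading is a chi-square or Fisher test on embryos, which ignores correlation between embryos in the same woman

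*Combined protocol and SAP*

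**What the plan says.** Section 10 (Outcome measures) states: "Implantation rate will be defined as the number of gestational sacs per the number of embryos transferred". Section 5.3.3 says that "one to three embryos will be transferred", so one woman can contribute up to three units to the denominator. Section 5.2 randomises women and stratifies by age: "The randomization will be stratified by the age (35-37, 38-39 and 40-42").

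Sections 3 and 10 both place implantation among the "pregnancy outcomes (rates of biochemical pregnancy, implantation, clinical pregnancy and miscarriage"). Both give a separate bracketed list of oocyte and embryo measures, and implantation is not in it.

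Section 12.3 has two rules for secondary efficacy. The first says "secondary efficacy parameters, such as pregnancy rate, miscarriage rate and other rates, will be analyzed using the Pearson" chi-square test or Fisher's exact test. The second covers measures "including the counts and rates of oocytes/embryos, will be analyzed using the Mann-Whitney U test". Neither names implantation or gives its unit of analysis. The missing-data rule in 12.3 does not mention it either. Section 12.1 reserves chi-square and Fisher for categorical variables and sets a two-sided 0.05 threshold. Section 12 contains no clustered, robust-variance or mixed-model method.

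**The concern.** Implantation is classed as a pregnancy outcome, so the first rule in 12.3 is its natural home. A chi-square or Fisher test needs counts, and the only counts in the definition are sacs and embryos. An analyst who follows the text would therefore probably build a two-by-two table of embryos.

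That test treats embryos as independent. Embryos transferred to one woman share her uterus, her age and her treatment cycle, so their outcomes may well be positively correlated. If they are, the test's standard error is too small. A borderline implantation result could be declared significant at 0.05 when a correct analysis would not support it.

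**Working it through.** **The plan's own figures.** None is given for implantation. The primary sample size does reproduce: 0.42 versus 0.33, two-sided 0.05, 80% power and pooled variance give 454 per arm; 454/(1 − 0.38) = 732.3, rounded up to 733 per arm, or 1466 in total. This point does not touch it.

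**Inputs from the documents.** One to three embryos per woman (5.3.3); three age strata (5.2); alpha 0.05 two-sided (12.1); 38% lost before transfer, since "the dropout rate before ET was 15% and the cycle cancellation rate was 23% in AMA women" (12.2).

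**Assumed inputs.** The documents do not give these:
- total ICC of 0.05, 0.1 or 0.3;
- percentages of women with one/two/three embryos of 70/30/0, 50/50/0, 20/70/10 or 10/60/30;
- mean implantation of 25%;
- equal age strata.

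An age gradient is plausible because section 2 notes that "aging adversely affects both oocyte quality and ovarian reserve". It matters because stratified randomisation balances the part of the correlation that age explains.

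**Formulas.** Let m be embryos per woman, μ1 = E(m), μ2 = E(m²), and p_s the implantation rate in stratum s. Let V = p̄(1 − p̄), B the variance of p_s across strata, W the mean of p_s(1 − p_s), and ρ = (ICC·V − B)/W. Let f be the share of the balanced women who reach transfer.

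Deff = [W(μ1 + ρ(μ2 − μ1)) + B(μ2 − f·μ1²)] / (μ1·V)

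True type I error = 2[1 − Φ(1.96/√Deff)]

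With no gradient B = 0, and Deff = 1 + (μ2/μ1 − 1)·ICC.

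**Worked case: mix 20/70/10, ICC 0.1.** μ1 = 0.2 + 1.4 + 0.3 = 1.9 and μ2 = 0.2 + 2.8 + 0.9 = 3.9.
- No gradient: Deff = 1 + 1.0526 × 0.1 = 1.105, and the error is 6.2%.
- Strong gradient (35/25/15%): V = 0.1875, B = 0.00667, W = 0.1808, ρ = 0.0668. With f = 1, Deff = [0.1808 × 2.0336 + 0.00667 × 0.29]/0.35625 = 1.038, and the error is 5.4%. With f = 0.62, 0.29 becomes 3.9 − 0.62 × 3.61 = 1.66, Deff = 1.063, and the error is 5.7%.

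**Type I error of the embryo-level chi-square, range over the four mixes:**

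| Setting | ICC 0.05 | ICC 0.1 | ICC 0.3 |
|---|---|---|---|
| No age gradient | 5.3–5.8% | 5.5–6.6% | 6.6–9.9% |
| Mild gradient (30/25/20%), f = 1 | 5.1–5.6% | 5.4–6.4% | 6.5–9.6% |
| Strong gradient (35/25/15%), f = 1 | 4.7–4.9% | 5.0–5.7% | 6.1–8.9% |
| Strong gradient, f = 0.62 | 4.9–5.2% | 5.2–6.0% | 6.3–9.3% |

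The age strata account for an ICC of B/V = 0.009 (mild) or 0.036 (strong).

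**In p-values.** An embryo-level p of 0.04 (z = 2.054) is corrected by dividing z by √Deff. At ICC 0.1 it becomes 0.045 to 0.054 with no gradient, and 0.040 to 0.049 with the strong one. At ICC 0.3 it becomes 0.054 to 0.084 and 0.049 to 0.078.

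**Simulation check** (beta-binomial, strong gradient, 20,000 trials per setting). The embryo-level test gave 5.1% to 5.5% (f = 1) and 5.1% to 6.2% (f = 0.62) at ICC 0.1, and 6.2% to 9.3% and 6.4% to 9.3% at ICC 0.3. A woman-clustered ratio test adjusted for age stratum gave 4.8% to 5.5% in every setting. Without the age covariate it fell to 4.0% to 4.8% at f = 1.

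**The case against.** The plan never states an embryo-level test; that is inferred. Section 12.3 sends oocyte and embryo rates to Mann-Whitney without repeating the list from sections 3 and 10, and section 10 defines those rates in the same ratio form as implantation. A per-woman ratio also fits poorly with the categorical variables for which 12.1 keeps chi-square. On that reading there is one value per woman and no clustering problem.

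The size of the effect also rests wholly on assumed inputs. It is negligible at ICC 0.05 with a steep age gradient and zero with single transfers. Only ICC 0.3 with mostly double or triple transfers brings it near 9% to 10%. Implantation is one of many secondary outcomes.

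Most of this stands. The woman-level reading cannot be excluded, so this is an unspecified analysis with a probable flaw, not an error the plan explicitly commits. But two sections list implantation outside the embryo family, which makes the chi-square reading the likelier. The two readings also compare different quantities: a pooled ratio, and a distribution in which every woman counts equally. Leaving the choice open is itself a gap.

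It is also true that the age covariate is not needed to prevent false positives, since omitting it makes the clustered test at most conservative. The reason to include it is to use the stratification and keep the size near 5%.

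**Conclusion.** The concern holds as a minor point, with medium confidence in the embryo-level reading. If implantation is tested on embryos, its true type I error is about 5.0% to 6.6% at ICC 0.1 and 6.1% to 9.9% at ICC 0.3, against a nominal 5%. At ICC 0.05 it runs from 4.7% to 5.8%. These figures depend on the assumed ICC, embryo mix, 25% implantation rate and age gradient. There is no inflation if the correlation is zero, if all transfers are single, or if one value per woman is analysed. The live-birth analysis, the sample size and the per-woman clinical pregnancy rate are unaffected.

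**What to change.** Add one sentence to section 12.3 that names implantation and analyses it with the woman as the cluster and age stratum as a covariate. Either the ratio of sacs to embryos with a woman-level robust standard error, or a logistic GEE clustered on woman (independence working correlation, robust standard errors), would do. State that Pearson chi-square and Fisher will not be applied to embryos.

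Mann-Whitney on per-woman rates, already in the plan for embryo rates, is an acceptable alternative. It weights women equally, so it does not compare the ratio defined in section 10. In simulation (454 per arm, no gradient, 10,000 trials, 25% versus 32%) its power was 71.8% to 88.5% across the four mixes at ICC 0.1, against 74.2% to 90.3% for the clustered ratio test: at most 2.4 points lower. At ICC 0.3 the two were within 0.3 points.

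The cost is one sentence and a different procedure call. The standard error for implantation changes by about 0% to 7% at ICC 0.1 (√1.136 = 1.066 at most) and grows by about 4% to 19% at ICC 0.3 (√1.092 = 1.045 to √1.409 = 1.187). Data collection and sample size do not change.

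### The planned miscarriage P value compares women selected by becoming pregnant after randomisation, so it is not a randomised comparison; report those rates descriptively, beside counts per randomised woman

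*Combined protocol and SAP*

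**What the plan says.** Section 10 (Outcome measures) lists miscarriage among the secondary pregnancy outcomes and fixes its denominators: "Miscarriage rate will be calculated among patients with biochemical pregnancies and patients with clinical pregnancies".

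Section 12.3 makes it a between-arm test: "secondary efficacy parameters, such as pregnancy rate, miscarriage rate and other rates, will be analyzed using the Pearson" chi-square test, or Fisher's exact test as appropriate. Section 12.1 sets the two-sided 0.05 threshold.

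Section 2 (Background) reports that an earlier trial by the same group had suggested that "the intervention of ZYP among advanced maternal aged women could significantly increase the clinical pregnancy rate during ART". It describes that result as a post hoc subgroup analysis without adequate power. It also cites a clinical report suggesting that "oral intake of ZYP around the luteal phase could significantly increase the embryo implantation rate".

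Two further places bear on the point. The missing-data rule in Section 12.3 covers live birth and "secondary outcomes (biochemical pregnancy, clinical pregnancy) in the ITT analysis will be imputed as not having an event"; miscarriage is not named. Table 6 defines a safety outcome without a denominator: "Pregnancy loss is defined as pregnancies that eventuate in spontaneous abortion or therapeutic abortion that occurred throughout pregnancy". No miscarriage rate per randomised woman is stated anywhere, and no caution is attached to the conditional comparison.

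**The concern.** Study drug starts before ovarian stimulation (Section 5.4), so whether a woman becomes pregnant is itself a possible effect of treatment. If ZYP produces pregnancies that would not have occurred on placebo, the pregnant women on ZYP are a mixture: those who would have been pregnant anyway, and those pregnant only because of the drug. Placebo has only the first kind. Randomisation does not balance these groups, and the planned tests make no adjustment.

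The error can go either way. Fragile extra pregnancies would make ZYP look as if it causes loss; robust ones would make it look protective. This matters more here than in most fertility trials, because the Background and the drug label (Section 5.4.4) present the product as a treatment for miscarriage. A significant result in either direction could easily be read as a causal effect on miscarriage.

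**Working it through.** **Inputs from Section 12.2:** live birth per transfer 0.42 (ZYP) and 0.33 (placebo); 454 women per arm with transfer; 80% power; alpha 0.05 (two-sided, Section 12.1); 38% dropout and cancellation; 733 randomised per arm.

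**Reproducing the plan's figure.** With pooled variance and no continuity correction,
n = [1.96·√(2·0.375·0.625) + 0.8416·√(0.42·0.58 + 0.33·0.67)]² / 0.09² = 453.04, rounded up to 454. Then 454/0.62 = 732.3, rounded up to 733. Both agree with the plan.

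**Assumptions, because the documents give no pregnancy or miscarriage rates.**
- Women who would be pregnant in either arm have loss risk m, identical in both arms, so the drug changes none of their losses.
- Women pregnant only on ZYP have loss risk e.
- No woman is pregnant on placebo only.
- Each pregnancy ends in live birth or miscarriage.
- Pregnancy rates are set to give live birth of 0.33 and 0.42 per transfer.

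**Formulas.**
- Placebo pregnancy rate: p0 = 0.33/(1 − m).
- ZYP pregnancy rate: p1 = p0 + 0.09/(1 − e).
- Conditional miscarriage rate: m on placebo; r1 = [p0·m + (p1 − p0)·e]/p1 on ZYP.
- Rejection probability: normal approximation to the two-proportion test with pooled variance (Pearson chi-square without correction), with N0 = 454·p0 and N1 = 454·p1 pregnancies.

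**Worked case, m = 0.20, e = 0.** p0 = 0.33/0.80 = 0.4125, so N0 = 187.3 with 37.5 losses. p1 = 0.4125 + 0.09 = 0.5025, so N1 = 228.1, also with 37.5 losses. The rates are 20.0% and 37.5/228.1 = 16.4%. The pooled rate is 75.0/415.4 = 0.180, giving a null SE of 0.0379 and an SE under the alternative of 0.0382. With d = −0.0358, rejection = Φ[(−1.96·0.0379 + 0.0358)/0.0382] plus a negligible upper tail = 16%.

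**Results at m = 0.20:**

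| Loss risk e in extra pregnancies | Losses/pregnancies, placebo | Losses/pregnancies, ZYP | Conditional rates | Rejection |
|---|---|---|---|---|
| 0% | 37.5/187.3 | 37.5/228.1 | 20.0% v 16.4% | 16% |
| 20% (same risk) | 37.5/187.3 | 47.7/238.3 | 20.0% v 20.0% | 5% |
| 40% | 37.5/187.3 | 64.7/255.4 | 20.0% v 25.3% | 26% |
| 50% | 37.5/187.3 | 78.3/269.0 | 20.0% v 29.1% | 60% |

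**Range over m = 0.15 to 0.30.** At e = 0 the apparent benefit is 2.8 to 4.8 points, with rejection of 13% to 21%. At e = 40% the apparent harm is 7.0 down to 2.4 points, with rejection of 43% down to 9%. At e = m rejection stays at 5%.

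**Would testing per randomised woman cure it?** Divide the losses by 733. At e = m = 0.20: 37.5/733 = 5.1% v 47.7/733 = 6.5%, with rejection of 21% (16% to 33% over the range of m). At e = 40%: 5.1% v 64.7/733 = 8.8%, with rejection of 80% against 26% for the conditional test. Only at e = 0 does it do better (5.1% in both arms, 5% against 16%).

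**The case against.** Miscarriage per pregnancy is the conventional measure and answers a natural question: the risk once pregnant. It is one of many secondary outcomes. The distortion vanishes if the extra pregnancies carry ordinary risk, and the documents give no evidence on that either way. The evidence that ZYP raises pregnancy is itself weak: the result in older women was post hoc and underpowered, and the implantation report is not described as concerning older women. Much of the pathway is already planned, since live birth, biochemical pregnancy and clinical pregnancy have an ITT imputation rule, so pregnancies without live birth follow roughly by subtraction. All of this stands. It limits the weight of the point but does not make the planned P value a randomised comparison. The subtraction also mixes miscarriage with other losses and with imputed outcomes.

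Three stronger readings are tempting, and none is supported:
- A reader might infer that the analysis will show harm or benefit where there is none. It may; the size and direction depend on an unknown loss risk.
- A reader might infer that the plan rules out any other miscarriage analysis. The denominator for pregnancy loss in Table 6 is unstated, so a per-randomised analysis is neither given nor excluded.
- A reader might infer that the test should simply move to all randomised women. That comparison is validly randomised, but it measures total losses, which rise when pregnancies rise, so it can penalise a drug for creating pregnancies.

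**Conclusion.** The point holds as a minor improvement. The planned miscarriage test compares groups selected after randomisation by an event the drug may influence, and no rate per randomised woman is stated beside it. On the plan's own live-birth assumptions and an assumed 20% base loss, the test rejects in 16% of trials when the extra pregnancies have no losses and in 26% when 40% of them are lost, although the drug changes no loss among women who would be pregnant in either arm. At equal risk the figure is the nominal 5%. These figures rest on assumed loss risks and on the simplifications listed in the working: they show what is possible and do not predict this trial's result.

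**What to change.** In Section 12.3:
- Report the two conditional miscarriage rates (per biochemical and per clinical pregnancy) as descriptive, with 95% CIs and no significance test.
- Add miscarriage as a count and percentage of all randomised women, with the between-arm difference and its 95% CI, in one table beside biochemical pregnancy, clinical pregnancy and live birth per randomised woman.
- Do not attach a significance test to the per-randomised miscarriage rate. State that it is to be read only together with live birth.
- Since the missing-data rule does not name miscarriage, say how pregnant women with unknown outcome are counted in that row.

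The cost is one table row and a few sentences, with no new data, visits or participants. The downside is that a conventional secondary measure loses its P value.
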